STUDY PROTOCOL

Title: The Effect of Mild Exercise While Receiving Chemotherapy on the Psychology of

the Cancer Patient

NCT Number: NCT06943638

Date: 31 July 2025

1. Background and Rationale

Cancer patients undergoing chemotherapy often experience heightened levels of anxiety. Non-pharmacological interventions such as mild physical activity may alleviate these symptoms. This study investigates whether a short, tailored exercise program can reduce anxiety levels in adult cancer patients.

2. Objectives

Primary Objective:

To assess the effect of a mild, individualized exercise program on state anxiety levels in cancer patients undergoing chemotherapy.

3. Study Design

This is a prospective observational cohort study conducted at the General Oncology Hospital of Kifissia "Agioi Anargyroi" in Athens, Greece.

4. Study Population

• Inclusion Criteria:

- o Age ≥ 18 years
- Receiving chemotherapy
- Ability to understand and provide informed consent

• Exclusion Criteria:

- Refusal to participate
- o Cognitive or sensory impairment affecting ability to engage
- o Inability to mobilize independently

5. Intervention

Participants receive 20-minute sessions of mild physical exercises designed by a

licensed physiotherapist, including warm-up, upper limb, lower limb, and stretching

routines. Sessions are tailored to each participant's physical condition and conducted

in person.

6. Outcome Measures

Primary Outcome:

Change in state anxiety level as measured by the Spielberger State-Trait

Anxiety Inventory (STAI-Y1) before and after the intervention.

7. Data Collection

The STAI-Y1 will be administered pre- and post-intervention. Demographic data

including age and gender will be collected at baseline.

8. Ethical Considerations

Ethics approval was granted by the Ethics Committee of the General Oncology

Hospital of Kifissia (Protocol #779/15-1-2024). Written informed consent will be

obtained from all participants.

9. Data Management and Confidentiality

Data will be anonymized and stored securely. Only study investigators will have

access to identifiable information. All analyses will use coded identifiers.

10. Study Timeline

• Start Date: 02 December 2024

End Date: 24 March 2025

STATISTICAL ANALYSIS PLAN

Title: The Effect of Mild Exercise While Receiving Chemotherapy on the Psychology of

the Cancer Patient

NCT Number: NCT06943638

Date: 31 July 2025

1. Purpose

This SAP outlines the pre-specified statistical methods for analyzing the impact of a mild exercise intervention on state anxiety levels among cancer patients undergoing chemotherapy.

2. Study Objectives (Statistical)

- Assess the change in STAI-Y1 anxiety scores before and after the intervention.
- Explore associations between age, gender, and anxiety score changes.

3. Study Variables

Primary Outcome:

Change in STAI-Y1 scores (post-intervention minus baseline)

Covariates:

Age, gender

4. Statistical Methods

Descriptive Statistics:

Summary statistics (mean, SD, median, IQR) will be calculated for all variables.

Inferential Tests:

- Wilcoxon signed-rank test to compare pre- and post-intervention anxiety scores (due to expected non-normal distribution).
- o Cohen's D for paired samples to assess effect size.
- Spearman's rank correlation to explore relationships between demographics and anxiety change.

5. Sample Size Estimation

Based on similar studies (e.g., Moraes et al., 2021), a minimum of 45 participants is estimated to provide 80% power to detect significant differences (α = 0.01).

6. Handling of Missing Data

Any missing questionnaire responses will be evaluated. If fewer than 5% of responses are missing, listwise deletion will be used. Otherwise, imputation methods may be considered.

7. Software

All analyses will be conducted using SPSS v29.

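### Does the SAP need a stated denominator for Cohen's D and a planned confidence interval for the change in STAI-Y1?

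*SAP*

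**What the plan says.** SAP section 2 sets the aim: "Assess the change in STAI-Y1 anxiety scores before and after the intervention". Section 3 names the primary outcome as a variable in its own right: "Change in STAI-Y1 scores (post-intervention minus baseline".

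Section 4 then plans:

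- descriptives: "Summary statistics (mean, SD, median, IQR) will be calculated for all variables";
- a paired Wilcoxon signed-rank test, chosen "due to expected non-normal distribution";
- Cohen's D "for paired samples to assess effect size";
- Spearman's "rank correlation to explore relationships between demographics and anxiety change".

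Section 5 gives the size: "a minimum of 45 participants is estimated to provide 80% power to detect significant differences", at an alpha of 0.01. Section 7 names SPSS v29 and no options. Neither document mentions a confidence interval or the denominator of D. The SAP is dated 31 July 2025; Protocol section 10 gives "End Date: 24 March 2025".

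**The concern.** Three things look wrong.

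1. A paired D can be a mean change over the SD of the differences, over the baseline SD, or over a pooled or averaged SD. The same data can give quite different values. The SAP is dated after the study ended, so an open choice could be made with the data in hand.
2. The objective is to assess a change, yet the plan lists a p-value and point summaries with no interval. With about 45 participants the uncertainty is not small.
3. The rank test is chosen because non-normality is expected, while the only effect size rests on a mean and an SD. The estimate that belongs to the signed-rank test is the Hodges-Lehmann one, and it is not planned.

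If these gaps left the result unreadable, the primary finding would be a p-value beside a number that could not be compared with other studies.

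**Working it through.** **Inputs from the documents.** n = 45, power 80%, alpha 0.01 (SAP section 5); mean, SD, median and IQR for all variables (section 4); change score as a study variable (section 3). The documents give no effect size, SD of change, pre/post correlation or sidedness. Where these are needed below, they are assumptions shown over a range.

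**The plan's own figure.** The 45 cannot be reproduced without an effect size, so solve backwards. With the normal approximation, two-sided, the standardized change on the difference SD is (2.576 + 0.842)/√45 = 0.51. The noncentral paired t gives 0.53, and the Wilcoxon test (efficiency 3/π) gives 0.54. One-sided, the three values are 0.47, 0.49 and 0.50. The 45 is plausible but unverifiable, and the way D is later reported does not alter it.

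**Size of the denominator question.** With equal pre and post SDs and correlation r, D on the difference SD divided by D on the baseline SD is 1/√(2(1 − r)):

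| assumed r | ratio | 0.50 on the baseline SD becomes |
|---|---|---|
| 0.3 | 0.85 | 0.42 |
| 0.5 | 1.00 | 0.50 |
| 0.7 | 1.29 | 0.65 |
| 0.9 | 2.24 | 1.12 |

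The ambiguity can be large, but the last row needs a correlation of 0.9, and at 0.5 there is none.

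**What can be recovered from the planned output.** Let M and S be the mean and SD of the change score.

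- D on the difference SD is M/S. Comparing this with the reported D shows whether that denominator was used.
- The 95% t-interval for the change is M ± t(44) × S/√45 = M ± 2.015 × S/6.708 = M ± 0.30 S. At 99% it is M ± 2.692 × S/6.708 = M ± 0.40 S.
- For an assumed S of 8, 10 or 12 points, the half-widths are 2.4, 3.0 and 3.6 (95%) and 3.2, 4.0 and 4.8 (99%).
- The interval for D on the difference SD needs only D and n, by inverting the noncentral t on 44 degrees of freedom. D = 0.5 gives 0.19 to 0.81 (95%) and 0.09 to 0.905 (99%); D = 0.3 gives 0.00 to 0.60 (95%).

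The interval that inverts the signed-rank test cannot be recovered, because it needs the individual differences.

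**Would a Hodges-Lehmann interval be better?** Simulations of 45 differences, SD 10, 3,000 runs each, 95% intervals. For symmetric differences the comparison is of half-widths:

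| distribution | Hodges-Lehmann half-width | t half-width |
|---|---|---|
| normal | 3.08 | 2.98 |
| t with 3 df | 2.24 | 2.79 |
| 10% contaminated normal | 2.61 | 2.96 |

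It is about 3% wider under normality, and 20% and 12% narrower with heavy tails. For skewed differences the comparison is of how often the interval covers the mean change:

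| distribution | Hodges-Lehmann | t |
|---|---|---|
| exponential | about 80% | 93% |
| gamma, shape 2 | about 87% | about 95% |

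Under skew the Hodges-Lehmann interval still covers its own target, the pseudomedian, about 94% to 95% of the time. That is neither the mean nor the median the SAP plans to report.

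**The case for a change.** The best case for amending is that the addition is cheap: two or three sentences, no new data, and an open denominator closed in a SAP that postdates the end of the study. The phrase about paired samples hints at the SD of the differences but does not settle it. A t-interval rebuilt by the reader is not the interval matching the planned test, and readers should not have to do the authors' arithmetic.

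Part of this stands. A report that names the denominator and prints an interval for the change in points is better than one that does not, and an analyst writing up these data would ordinarily supply both. The post-study date is a fair reason for saying openly what was chosen and when. But the choice cannot stay hidden: the mean and SD of the change are committed to, so a D on some other SD would fail to match their ratio. The mismatch between a rank test and a mean-based effect size is one of style. The test is valid, and the median and IQR are planned alongside.

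**Conclusion.** No change to the plan follows. The SAP is silent on the denominator of D and on intervals, but followed as written it delivers a valid signed-rank test together with the mean, SD, median and IQR of the change. From these, D on the difference SD and a t-interval of ± 0.30 SD of change (95%, n = 45) follow directly. Naming the denominator and printing the interval are reporting details that analysts fill sensibly; they change no test, p-value, sample size or conclusion. Adopting Hodges-Lehmann as the effect estimate would be a fair trade-off rather than a correction: it gains precision with heavy tails and targets a different quantity under skew, which the SAP's expectation of non-normality does not rule out.

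This rests on the change score being summarized as sections 3 and 4 together imply, and on about 45 participants with complete pairs. The half-widths in points depend on assumed SDs of 8 to 12, and the denominator ratios on assumed correlations of 0.3 to 0.9.

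### SAP section 6: if a response means an item, the 5% trigger does not hold patient loss to about 5%, and listwise deletion can discard pre/post pairs that could be scored

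*SAP*

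**What the plan says.** SAP section 6 is the only text on missing data in either document. It has three steps:

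- The opening step is a general review: "Any missing questionnaire responses will be evaluated".
- Below the threshold the action is fixed: "If fewer than 5% of responses are missing, listwise deletion will be used".
- At or above the threshold nothing is fixed: "Otherwise, imputation methods may be considered".

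It does not define a response, gives no rule for scoring a form with a blank item, sets no limit on the number of patients deleted, and names no imputation method.

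The analysis is paired. The primary outcome in SAP section 3 begins "Change in STAI-Y1 scores (post-intervention minus baseline", and Protocol section 7 says "The STAI-Y1 will be administered pre- and post-intervention". Each patient therefore needs two usable scores. SAP section 5 says that "a minimum of 45 participants is estimated to provide 80% power to detect significant differences", at α = 0.01, and states no allowance for loss. Protocol section 10 gives "End Date: 24 March 2025"; the SAP is dated 31 July 2025.

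**The concern.** The trigger and the action use different units. A percentage of missing answers is compared with 5%, and the consequence falls on whole patients. With two multi-item forms per patient, a low rate of blank items can touch a much larger share of patients. If each blank voids a score, the rule deletes pairs that are almost fully observed, and the result then describes only patients who left nothing blank.

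Precision and power are at stake, and so is discretion. Two analysts following section 6 could analyse different sets of patients. At 5% or more, the text leaves open whether anything is imputed, and how. On the documents' dates, data collection had ended before the SAP date, so lost pairs cannot be replaced.

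**Working it through.** **Inputs from the documents.** Minimum 45 participants, 80% power, α = 0.01 (SAP section 5); two forms per patient (Protocol section 7); trigger below 5% (SAP section 6).

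**Assumed, not in the documents.** k = 20 items per form; exactly 45 patients; within-patient correlation of blanks ρ = 0.1 to 0.8; two-sided testing.

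**The plan's own figure.** The 45 cannot be reproduced, because no effect size or SD is given. Solving backwards with a paired t-test (two-sided 0.01, 80% power, n = 45) gives a standardised effect of about 0.53. It is used below only to translate lost pairs into power. The planned test is Wilcoxon; a version scaled by its asymptotic efficiency gives nearly the same power after loss.

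**Item reading, one blank voids the form.** Total items = 45 × 2 × 20 = 1,800. The trigger is met up to 89 blanks (89/1,800 = 4.94%).

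- *Limits at 89 blanks.* Packed as tightly as possible: 89/40, rounded up, is 3 patients (3/45 = 6.7%). Spread as widely as possible: all 45 pairs are lost.
- *1% missing, one blank per patient.* 18 blanks leave 45 − 18 = 27 pairs (40% lost).
- *1% missing, independent blanks.* 45 × (1 − 0.01)^40 = 45 × 0.669 = 30.1 pairs (33% lost; power about 56%).
- *Clustered blanks (beta-binomial).* With s = 1/ρ − 1, a = m·s and b = (1 − m)·s, pairs kept = 45 × B(a, b + 2k)/B(a, b). Example: m = 1% and ρ = 0.2 give s = 4, a = 0.04, b = 3.96, and 40.7 pairs.

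Proration at 90% answered allows at most 2 blanks per 20-item form. Pairs kept = 45 × Σ C(20,i)·C(20,j)·B(a + i + j, b + 40 − i − j)/B(a, b), summed over i, j = 0, 1, 2.

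| Pairs kept of 45 | ρ = 0.1 | 0.2 | 0.4 | 0.6 | 0.8 |
|---|---|---|---|---|---|
| 1% missing, strict deletion | 38.5 | 40.7 | 42.6 | 43.5 | 44.1 |
| 1% missing, proration | 43.4 | 43.4 | 43.8 | not needed | not needed |
| 4.9% missing, strict deletion | 20.7 | 27.3 | 34.3 | about 38 | about 41 |
| 4.9% missing, proration | 36.3 | 37.2 | 39.0 | not run | not run |

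At 1% missing, strict deletion loses between (45 − 38.5)/45 = 14% and (45 − 44.1)/45 = 2% of pairs. At ρ = 0.1 power is about 71%. At ρ = 0.6 or more the strict rule costs at most 1.5 pairs at 1% missing.

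The item count is not critical: at 1% missing and ρ = 0.1 to 0.4, strict deletion leaves 40 to 43 pairs with 10 items and 36 to 42 with 40 items.

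**Form reading.** Below 5% allows 4 of 90 forms (4.4%; 5 of 90 is 5.6%). At worst these belong to four patients: 41 pairs, power about 75%.

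**Patient reading.** Below 5% allows 2 of 45 (4.4%; 3 of 45 is 6.7%): 43 pairs, power about 78%. Proration does not help under either of these two readings.

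**Cost of proration in accuracy.** Error SD as a fraction of score SD = √{[(1 − r)·b·k/(k − b)] / [k + k(k − 1)r]}, where b is now the number of blanks and r the mean inter-item correlation. With k = 20, b = 2 and r assumed at 0.2, 0.3 or 0.5, this gives 0.14, 0.11 or 0.07.

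**Timing.** 24 March to 31 July 2025: 7 + 30 + 31 + 30 + 31 = 129 days.

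**The case against.** The loss needs several conditions together: a response means an item, one blank voids a form, blanks occurred, and enrolment was not far above 45. None is documented. SAP section 5 gives 45 as a minimum, and section 3 defines the outcome on scores, so deletion could be meant to act on scored variables only. Under the form and patient readings the loss is trivial. The item count, the correlation range and the effect size come from outside the documents, and the correlation drives the result: strong clustering nearly removes the problem at 1% missing. The instrument may have its own rule for blank items, which cannot be seen from here, and the 90% cut-off is a judgement.

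All of that stands, and it limits the size of the point. It does not close the gap. Section 6 still leaves its unit and its treatment of a blank item unstated, and still names no method at 5% or more.

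A reader might go further and infer that the trial lost a third or more of its pairs. The documents do not support that: they report no missing items and no number enrolled. A reader might also infer from the dates that the rule was chosen with the data in view. The dates show only that the SAP is dated after the study end; neither document says whether data had been examined.

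**Conclusion.** The point holds conditionally, as a minor one. If a response is an item and a blank voids the score, the 5% trigger does not bound patient loss at about 5%. With 1% of items missing, 27 pairs remain in the most scattered case and about 38 to 44 if blanks cluster within patients. Near the trigger, even the tightest packing removes 3 of 45. Some of these pairs could be scored from the answered items. Under the other two readings at least 41 or 43 pairs remain and little turns on it. The pair counts rest on 20 items, 45 patients and an assumed correlation. They illustrate a possible loss and do not forecast one; enrolment above 45 would offset it. What needs no assumption is that the unit, the scoring of incomplete forms and the method at 5% or more are all unspecified.

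**What to change.** Rewrite SAP section 6 as follows.

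- (a) Define a response as one STAI-Y1 item. The percentage of missing items is then reported as a description and no longer decides who is deleted.
- (b) After applying the scoring key, score a form from its answered items by person-mean proration when at least a stated share is answered, instead of deleting the patient. 90% is an example and a judgement; use the instrument's own rule if it has one.
- (c) Treat any other form as missing. Run the planned Wilcoxon test on all patients with both scores, and report exclusions with reasons, separately for pre and post.
- (d) Report strict complete-item pairs as a sensitivity analysis.
- (e) Replace the optional imputation with a named sensitivity analysis whenever scores are missing, secondary to the Wilcoxon test: multiple imputation of the missing score from the patient's other score, age and gender, reporting the mean change with its confidence interval. The demographics are planned data ("including age and gender will be collected at baseline"). Count patients with neither form, and do not impute them.
- (f) Date the change and state whether data had been seen. If the current rule has already been applied, report both results and label the prorated one post hoc.

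The cost is SAP wording, a few lines of scoring code and two extra runs on data already collected. The downsides are that proration assumes unanswered items resemble answered ones, imputation assumes missing scores are predictable from those three variables, and the change may be post hoc and must be disclosed. Neither step recovers patients with no forms.

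### Does the open-ended imputation clause in SAP section 6 undermine the primary analysis?

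*SAP*

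**What the plan says.** SAP section 1 opens with "This SAP outlines the pre-specified statistical methods for analyzing the impact of a mild exercise intervention". Section 4 names two results for the primary outcome: a "Wilcoxon signed-rank test to compare pre- and post-intervention anxiety scores", and Cohen's d "for paired samples to assess effect size".

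Section 6 is the whole of the missing-data plan. It begins "Any missing questionnaire responses will be evaluated" and continues "If fewer than 5% of responses are missing, listwise deletion will be used. Otherwise, imputation methods may be considered". It names no imputation model, number of imputations, pooling rule or sensitivity analysis, and it does not say whether the percentage counts items, forms or participants.

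Section 5 says that "a minimum of 45 participants is estimated to provide 80% power to detect significant differences", with alpha 0.01. It gives no effect size or sidedness. Neither document gives an expected missing rate.

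The SAP carries "Date: 31 July 2025". Section 10 of the protocol gives "End Date: 24 March 2025".

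**The concern.** Three features together look troubling. Section 1 promises methods fixed ahead of time, while section 6 leaves one of them to judgement above a threshold. The threshold has no unit, so the same data could fall on either side of it. And the only date on the SAP is later than the stated end of the study (7 + 30 + 31 + 30 + 31 = 129 days from 24 March to 31 July 2025), so the documents do not show that the choice would be made without sight of the data.

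At stake are the Wilcoxon p-value and Cohen's d. Filling each missing post score with one value and then treating it as observed adds pseudo-observations. The spread of the changes shrinks, the p-value falls and d rises, with no new information. A literal reading of section 6 allows this.

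**Working it through.** **The plan's own figure.** With no effect size stated, 45 can only be solved backwards. Two-sided, normal approximation: 2.576 + 0.842 = 3.417 (before rounding), and 3.417/√45 = 0.51, the standardised mean change that 45 pairs would detect with 80% power at 0.01.

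**The unit of the 5% rule.** Take whole post forms as missing among 45 participants, hence 90 forms.

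| Missing post forms | Share of participants | Share of forms |
|---|---|---|
| 2 | 4.4% | 2.2% |
| 3 | 6.7% | 3.3% |
| 4 | 8.9% | 4.4% |
| 5 | 11.1% | 5.6% |

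The readings disagree only at 3 or 4. Counting items gives the same share as counting forms when whole forms are lost, because the number of items cancels.

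**Type I error.** Assumptions: 45 participants, no true change, bivariate normal scores, post scores missing completely at random, two-sided Wilcoxon test at 0.01, 200,000 replicates (Monte Carlo SE 0.0002–0.0005). Results at pre/post correlation 0.6:

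| Missing | Complete pairs | Post-mean | Regression | Mean-change | Smallest p of the four |
|---|---|---|---|---|---|
| 3 | 0.0090 | 0.0115 | 0.0150 | 0.0174 | 0.0194 |
| 5 | 0.0088 | 0.0130 | 0.0196 | 0.0250 | 0.0274 |
| 9 | 0.0088 | 0.0171 | 0.0359 | 0.0535 | 0.0574 |

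Over correlations 0.3 to 0.8, the single-value methods span about 0.011–0.017, 0.012–0.025 and 0.016–0.055. Multiple imputation of the post score from baseline (20 imputations, mean change pooled by Rubin's rules, 20,000 replicates, SE 0.0007) gives 0.0090 at 5 missing and 0.0090 at 9.

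If single items are blank instead (20 items per form assumed, 5–20% missing), scaling up from the person's own answered items gives 0.007–0.008, the same as with full data. Filling with the item mean gives 0.011–0.034.

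**Poor method or free choice?** Going from mean-change imputation alone to the smallest of four p-values adds 0.0274 − 0.0250 = 0.0024 at 5 missing and 0.0574 − 0.0535 = 0.0039 at 9. Against that most inflating method, nearly all the inflation comes from the method itself and would remain if it were named in advance.

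**Cohen's d.** Filling m scores with the mean change leaves the mean and the sum of squares unchanged, but moves the divisor from 44 − m to 44. So d is multiplied by √(44/(44 − m)): 1.036, 1.062 and 1.121 for m = 3, 5 and 9.

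**The price of requiring complete pairs.** Power falls from 80% at 45 pairs:
- 40 pairs: 3.417 × √(40/45) − 2.576 = 0.646, or 74%.
- 36 pairs: 3.417 × √(36/45) − 2.576 = 0.481, or 68%.

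Suppose 20% are missing and the log-odds of missing rise by 1 per SD of baseline anxiety. Complete-pair mean change is then off by 0.122, 0.070 and 0.035 score SD at correlation 0.3, 0.6 and 0.8, and its type I error is about 0.021, 0.016 and 0.014.

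**The case for a change.** The strongest case for a change is that permitted methods differ several-fold in type I error, the plan does not choose among them, and the choice may come after someone has looked at the missing data. A few sentences would close the gap with no new data, since baseline score, age and gender are already collected. Pooled multiple imputation is not a complete answer either. The 0.0090 belongs to a pooled mean change, not to the Wilcoxon test that section 4 names, and taking the median Wilcoxon p-value across imputations gave about 0.012–0.021 in runs with 5–25% missing. When missingness depends on baseline, single-value imputation does worse than complete pairs: 0.026–0.117 against 0.021–0.030 in separate runs at 20% missing (correlation 0.5–0.7).

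Much of this stands. Section 6 names no method, its unit is undefined, and mean-change imputation would be a bad choice. But permitting a method by silence is not adopting it. An analyst who considers imputation and declines it is left with complete pairs, which a paired test uses anyway and which section 6 already prescribes below 5%. At 3 or 4 missing forms, where the unit decides the branch, that analyst gets the same result on either reading.

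The obvious replacement, complete pairs at any missing share, exchanges one weakness for another. It relegates imputation from baseline to a supporting role in the setting where that imputation helps. The dates leave the timing unverified but do not show that data had been seen, and they are a separate matter from how missing scores are handled.

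**Conclusion.** No change follows. This is unwritten detail that a competent analyst fills sensibly, and fixing it more tightly means a trade-off between methods with no clear winner. Inflation of any size needs three things together: more than a few missing post scores, single-value imputation, and analysis of the filled values as observed. The plan asks for none of these. Up to 10% missing, runs with rounded scores at correlation 0.6 put single-value methods at no more than about 0.018. The 0.05 level appears only with mean-change imputation at about 20% missing.

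The figures rest on assumptions the documents do not supply: a two-sided 0.01 test (0.01 is stated only for the sample size), normal scores, pre/post correlation 0.3–0.8, and missingness completely at random except where stated. How often section 6 would be invoked cannot be judged, because no missing rate is given.
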